5.3 Treatment Assignment Procedures

5.3.1 Randomization Procedures

Since this is a sampling study with no therapeutic intervention or investigation, there are no randomization procedures.

5.3.2 Reasons for Delaying Study-Related Procedures

Study related laboratory draws will be delayed or deferred if the investigator believes that obtaining them might increase subject risk [e.g., at risk of a packed red blood cell (PRBC)]

transfusion due to the removal of blood for the study; however, if the subject would receive a transfusion of packed red blood cells even if the study-related labs were not obtained, then this would not be considered a situation of increasing subject risk]. Additionally, a study-related laboratory specimen that is unevaluable due to clotting or laboratory related issues will not be repeated. If a study related laboratory draw is delayed or deferred, study staff will document this on a source document.

5.3.3 Reasons for Withdrawal

The criteria for discontinuations during the study include:

- Study subject (parent/legal guardian) wishes to withdraw
- Non-compliance with study procedures
- Trial termination (by UAB, , FDA, DMID, NIAID, NIH, or agreement of all investigators)
- Any other reason which, in the opinion of the investigator, precludes the study subject's participation in the study. The principal investigator must call the Protocol Chair prior to discontinuing a study subject for this reason.

5.3.4 Handling of Withdrawals

Study subjects may withdraw voluntarily from participation in the study at any time. If a study subject withdraws or is discontinued from the study at any time prior to completion of the study, the reason for this decision will be recorded on the eCRFs. If subject withdraws before collection of the pharmacokinetic collection, this subject may be replaced (see Section 4).

5.3.5 Termination of Study

The UAB Central Unit and NIH have the right to terminate this study at any time. Reasons for terminating the study may include, but are not limited to, the following:

- Study subject enrollment is unsatisfactory
- Data recording is inaccurate or incomplete
- Investigators do not adhere to the protocol or applicable regulatory guidelines in conducting the study.

6 STUDY INTERVENTION/INVESTIGATIONAL PRODUCT

None.

This is a sampling study with no therapeutic intervention. Only subjects who receive intravenous ganciclovir as practice of medicine will be eligible to enroll. Intravenous ganciclovir will not be provided under this protocol.

7 STUDY SCHEDULE

7.1 Screening

There are no screening procedures for this study. Potential subjects will be identified by the site investigators and the study coordinators. Informed consent signed by study subject's parent(s) or guardian(s) must be obtained prior to study enrollment.

7.2 Enrollment/Baseline

7.2.1. Baseline Assessment (Period 1: Study Assessment Day 1 through Study Assessment Day 3, unless broader window specified)

- Confirm that informed consent has been obtained from parent or legally authorized representative
- Document baseline demographics (see Section 8.1.1; Window: Birth through Study Assessment Day 3)
 - Gestational age at delivery
 - Date of birth
 - Day of life at initiation of IV ganciclovir therapy
 - Gender
 - Race
 - Ethnicity
 - Birth weight
 - Weight at enrollment
 - Length in centimeters at enrollment
 - Reason ganciclovir being administered
 - Ganciclovir dose and dosing frequency
 - Manufacturer of the ganciclovir lot utilized at the treating facility
 - Date ganciclovir therapy was initiated
- Hematology labs (see Section 8.2; Window: Birth through Study Assessment Day 3)
 - WBC with differential, hemoglobin, and platelet count, if being drawn for clinical reasons; any laboratory value obtained during the window will suffice, with an effort being made to capture the most abnormal value
- Chemistry labs (see Section 8.2; Window: Birth through Study Assessment Day 3)
 - AST and ALT, if being drawn for clinical reasons; any laboratory value obtained during the window will suffice, with an effort being made to capture the most abnormal value

- Serum Creatinine (see Section 8.2.)
 - To be drawn on the calendar day that ganciclovir PKs are being drawn (Window: Study Assessment Day 1 through Study Assessment Day 5)
 - Required amount of whole blood for serum creatinine is 0.25 mL
- Ganciclovir pharmacokinetics (see Section 8.2.2.2.)
 - Ganciclovir concentrations will be obtained with one of the Study Assessment Dose 3, 4, 5, 6, 7, or 8 (Window: Study Assessment Day 1 through Study Assessment Day 5)
 - Timepoints for pharmacokinetic draws: 0h (immediately prior to IV ganciclovir dose; window: -15 min), 1h (immediately after the end of the IV ganciclovir dose; window: +15 min), 2-3h, 5-7h, and 10-12h
 - Required amount of whole blood for plasma ganciclovir determination at each timepoint is 200 μ L (0.2 mL)
- Virology specimens (see Sections 8.2.2.1.)
 - Blood for CMV quantitative PCR will be obtained (required amount of whole blood for CMV PCR is 0.5 mL)
 - If obtainable, urine for CMV detection will be collected non-invasively (e.g., bagged, from indwelling foley catheter, excess clinical specimen, etc.)
- Clinical treatment ganciclovir dosing information
 - mg/dose
 - Dosing interval
 - Patient weight
- PRBC transfusion documentation on eCRF
- Study Assessment ganciclovir dosing information
 - mg/dose
 - Dosing interval
 - Subject weight

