3 OBJECTIVES

3.1 Study Objectives

Primary:

- To define the pharmacokinetics of ganciclovir in premature (< 32 weeks gestational age at birth) infants

Secondary:

- To assess changes in quantitative viral DNA in whole blood as a function of ganciclovir pharmacokinetics
- To assess clearance of CMV in urine as a function of ganciclovir pharmacokinetics

Exploratory:

- To assess development of neutropenia as a function of ganciclovir pharmacokinetics
- To determine the potential for the development of resistance to ganciclovir as a function of pharmacokinetics, dose, age, and duration of therapy

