4 STUDY DESIGN

This is an open-label, multi-center, clinical sampling study of ganciclovir pharmacokinetics and pharmacodynamics of ganciclovir in premature infants undergoing antiviral therapy for CMV. Only those subjects who receive ganciclovir for clinical reasons will be enrolled. The decision to initiate ganciclovir therapy will be made by the attending physician based upon his/her clinical decision to treat virologically-confirmed CMV infection; infants receiving such therapy and meeting entry criteria will then be eligible for this study. Therefore, ganciclovir will be dispensed from the institution's pharmacy and not provided under this protocol.

Subjects meeting enrollment criteria will be entered into this clinical trial. Following enrollment, subjects will be stratified by gestational age and by chronologic age as follows: 1) \leq 27 weeks 6 days gestational age at birth and \leq 30 days chronologic age at study enrollment; 2) \leq 27 weeks 6 days gestational age at birth and $>$ 30 days chronologic age at study enrollment; 3) \geq 28 weeks 0 days gestational age at birth and \leq 30 days chronologic age at study enrollment; 4) \geq 28 weeks 0 days gestational age at birth and $>$ 30 days chronologic age at study enrollment. The total sample size across these four cohorts is 32 subjects. Subjects in each cohort with inadequate pharmacokinetic data for analysis (e.g., due to dropping out of the study before PK assessments are performed, or blood sampling obtained but is inadequate for analysis) may be replaced and will not count toward the total of 32 subjects. Additionally, enrollment of an additional 2-3 subjects may be allowed for operational reasons.

Treatment Day 1 is the calendar day when the first dose of intravenous ganciclovir was administered to the study subject for clinical care, and Treatment Dose 1 corresponds to the first dose of intravenous ganciclovir the patient receives under clinical care. Study Assessment Dose 1 is the first dose of intravenous ganciclovir the subject receives following enrollment on the trial, and Study Assessment Day 1 is the calendar day when Study Assessment Dose 1 is administered. Both Treatment Day 1 and Treatment Dose 1 can coincide with or precede study enrollment; Study Assessment Day 1 and Study Assessment Dose 1 by definition will follow study enrollment, and may or may not equate with Treatment Day 1 and Treatment Dose 1. Typically, ganciclovir is administered twice per day in these infants.

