Both whole blood for CMV PCR and urine for CMV assessment will be obtained serially through Study Assessment Period 7 as long as the subject is receiving intravenous ganciclovir therapy (that is, until the ganciclovir is permanently discontinued). These specimens will be used to determine viral load and, as indicated, ganciclovir resistance. At each sample collection time, urine will be split into two aliquots. These aliquots will be available for CMV detection as appropriate, based upon whole blood viral loads. Specimens will then be available for subsequent testing for ganciclovir resistance in the UAB Virology Resistance Laboratory. Since ganciclovir is a renally excreted drug, serum creatinine will be drawn for the research protocol on the day that the ganciclovir pharmacokinetic specimens are obtained in order to calculate creatinine clearance using a method such as the modified Schwartz formula, and thus correlate ganciclovir clearance with renal function. Otherwise, data from hematology assessments (WBC count and differential, hemoglobin, platelet count) and from chemistry labs (serum creatinine, ALT, and AST) will be recorded on the study case report forms each study assessment period if they are being obtained for clinical reasons, but will not be drawn only for the purposes of the study. Ganciclovir dosing information (mg/dose, dosing interval, and subject weight) will be recorded on the day of the pharmacokinetic blood draws. Once a subject is successfully enrolled into the study the ganciclovir dosing information (mg/dose and dosing interval) will be recorded from the start of clinical treatment of ganciclovir until date of enrollment. After enrollment ganciclovir dosing information (mg/dose and dosing interval) will be captured from Study Assessment Period 1 through the Study Assessment Period 7; as long as the subject is receiving intravenous ganciclovir therapy.

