7.3 Follow-up

7.3.1. Period 2 (Study Assessment Day 4 through Study Assessment Day 10)

Documentation of receipt of PRBC transfusion(s) will be provided on an eCRF. If the study subject has NOT received ≥ 10 PRBC transfusions (see Section 9.3.1), proceed with required assessments.

Required assessments [following confirmation that subject is still receiving ganciclovir (e.g., that the ganciclovir has not been permanently discontinued)]: 1) virology blood

specimens for CMV viral load (required amount of whole blood for CMV PCR is 0.5 mL); 2) CMV detection from noninvasive urine specimen (if obtainable); 3) ganciclovir dosing information (mg/dose, dosing interval, subject weight).

Optional assessments (if being drawn for clinical reasons; any laboratory value obtained during the window will suffice, with an effort being made to capture the most abnormal value): 1) hematology labs (WBC with differential, hemoglobin, platelet count); 2) chemistry labs (AST, ALT); 3) serum creatinine.

Study Assessments (as described)	Optional Assessments*
Virology blood specimens for CMV viral load	Hematology labs (WBC with differential, hemoglobin, platelet count)
If obtainable, CMV detection from noninvasive urine specimen (e.g., bagged, from indwelling foley catheter, excess clinical specimen, etc.)	Chemistry labs (AST, ALT)
Ganciclovir dosing information (mg/dose, dosing interval, subject weight)	Serum creatinine

* If being drawn for clinical reasons; any laboratory value obtained during the window will suffice, with an effort being made to capture the most abnormal value

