Ganciclovir pharmacokinetics		X ^h		X ^{i,j}			
Virology blood specimens for CMV viral load ^k	X ^l	X ^l	X ^l	X ^l	X ^l	X ^{l,m}	X ^{l,n}
CMV detection from noninvasive urine specimen	X ^o	X ^o	X ^o	X ^o	X ^o	X ^o	X ^o
Ganciclovir dosing information	X ^p	X ^p	X ^p	X ^p	X ^p	X ^p	X ^p
PRBC transfusion assessment	X ^q	X ^q	X ^q	X ^q	X ^q	X ^q	X ^q

Assessment for AEs or SAEs		X	X	X	X	X	X
Total volume of blood required for study procedures	1.75 mL	0.5 mL	0.5 mL	0.5 mL or 1.5 mL ⁱ	0.5 mL	0.5 mL	0.5 mL

a) Data and specimens in this column to be captured if subject still receiving ganciclovir as clinical treatment

b) Gestational age at delivery, date of birth, day of life at initiation of IV ganciclovir therapy, gender, race, ethnicity, birth weight, weight at enrollment, length in centimeters at enrollment, reason ganciclovir being administered, ganciclovir dose and dosing frequency, manufacturer of the ganciclovir lot utilized at the treating facility, date ganciclovir therapy was initiated

c) Window: Birth through Study Assessment Day 3)

d) WBC with differential, hemoglobin, platelet count. Optional laboratory draws are not required by the protocol, and so no documentation on a source document will be required.

e) If being drawn for clinical reasons; any laboratory value obtained during the window will suffice, with an effort being made to capture the most abnormal value. Optional laboratory draws are not required by the protocol, and so no documentation on a source document will be required.

f) AST, ALT. Optional laboratory draws are not required by the protocol, and so no documentation on a source document will be required.

g) To be drawn on the calendar day that ganciclovir PKs are being drawn. Study related laboratory draws will be delayed or deferred if the investigator believes that obtaining them might increase subject risk. Additionally, a study-related laboratory specimen that is unevaluable due to clotting or laboratory related issues will not be repeated. If a study related laboratory draw is delayed or deferred, study staff will document this on a source document.

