3.3. Functionality of the enrollment component of the eDES

- 3.3.1 When preparing to enroll a subject, the end user will select “New Subject”. The PID #1 will be assigned prior to entering eligibility criteria.
- 3.3.2 The end user will have the option to save or lock responses to entry criteria
 - 3.3.2.1 **Save:** data entered will be saved but will not be used to enroll/randomize a subject into the study and will not activate a screening notification email. The responses can be updated and edited as needed.
 - 3.3.2.2 **Lock:** the user has determined the eligibility data entered into the database are acceptable, and believe successful screening enrollment can occur. After locking, the data cannot be altered.
 - 3.3.2.3 Should a site need to alter responses to the screening entry criteria, the end user must request an unlock of the specific field in question. The PD or designee will unlock the form and permit the data to be amended. If this request takes place after the subject has started study required activities, the user may need to amend more than the entry criteria. This will require a meeting.
- 3.3.3 The enrollment criteria can be locked if all inclusion criteria are not met. However, no additional eCRFs will be available for use, since the subject did not meet enrollment criteria.
- 3.3.4 Enrollment schematic
 - 3.3.4.1 Enrollment in this protocol will be stratified based on gestational age and enrollment age. The groups are as follows:
 - 1) ≤ 27 weeks 6 days gestational age at birth and ≤ 30 days chronologic age at study enrollment;
 - 2) ≤ 27 weeks 6 days gestational age at birth and > 30 days chronologic age at study enrollment;
 - 3) ≥ 28 weeks 0 days gestational age at birth and ≤ 30 days chronologic age at study enrollment;
 - 4) ≥ 28 weeks 0 days gestational age at birth and > 30 days chronologic age at study enrollment.
 - 3.3.4.2 Enrollment will cease after 8 subjects are enrolled in a group.
- 3.3.5 Functions that occur after successful enrollment
 - 3.3.5.1 Confirmation of successful enrollment will appear on the computer screen immediately.
 - 3.3.5.2 Email notification of successful enrollment will be sent to key study personnel immediately to the site and others as designated by the PD or designee. The notification will include PID#1,#2, site number, PI name.

- 3.3.6 Failure to successfully complete enrollment of a subject

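### The baseline neutrophil value can predate or follow the start of ganciclovir, and later values depend on how often infants are tested, so the exploratory neutropenia analysis lacks a pre-treatment reference

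*Protocol*

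**What the plan says.** Protocol 3.1 lists as an exploratory objective: "To assess development of neutropenia as a function of ganciclovir pharmacokinetics". Section 3.2.3 makes the matching endpoint a correlation of plasma concentrations with neutropenia, also exploratory.

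The Period 1 blood count is defined in Protocol 7.2.1: "Hematology labs (see Section 8.2; Window: Birth through Study Assessment Day 3". It is recorded only if drawn for clinical reasons, and "any laboratory value obtained during the window will suffice, with an effort being made to capture the most abnormal value". Appendix A footnotes c and e repeat this, as do the same footnotes to the schedule in SAP section 6.

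On the start of treatment, Protocol section 4 says: "Both Treatment Day 1 and Treatment Dose 1 can coincide with or precede study enrollment". It also defines Study Assessment Day 1 as the calendar day of the first dose after enrolment. Inclusion criterion 3 requires that the infant is already on intravenous ganciclovir and sets no limit on earlier treatment.

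From Period 2 on, haematology falls under "Optional assessments (if being drawn for clinical reasons; any laboratory value obtained during the window will suffice". Section 4 says that these counts are recorded if available "but will not be drawn only for the purposes of the study". Appendix A footnote e adds: "Optional laboratory draws are not required by the protocol, and so no documentation on a source document will be required".

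The analysis (Protocol 11.4; SAP Appendix B) is a GEE for repeated binary data relating neutropenia to plasma concentration, with unnamed covariates. Neither text sets a neutropenia threshold, says how the Period 1 value is used, or mentions the number of tests.

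**The concern.** Studying the development of neutropenia requires knowing each infant's state before the drug. The Period 1 value does not reliably give that. In an infant enrolled at more than 30 days of age it may be a low count from the first days of life. In an infant treated for some days before enrolment it may be a drug effect. Both are recorded in the same way.

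The later values have a related problem. If the lowest of several counts is recorded, an infant tested daily has more chances to fall below any threshold than one tested weekly. If testing follows illness severity, and severity follows renal function and so exposure, part of an apparent link between exposure and neutropenia could come from testing.

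Protocol 2.2 expects the data to help limit toxicity in future premature infants, and neutropenia is the only drug toxicity named in the objectives. Protocol 2.1 cites Grade 3 or 4 neutropenia in about two-thirds of neonates given six weeks of ganciclovir, so on-drug low counts are a realistic prospect.

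**Working it through.** The plan states no figure on this point, so there is none to reproduce. The check has two parts.

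**1. What the Period 1 value can be.** Put the definitions on one time line:

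- The window opens at birth and closes at the end of Study Assessment Day 3.
- Treatment Dose 1 can fall on or before the day of enrolment.
- Study Assessment Day 1 is by definition a dosing day.

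The window therefore always includes some on-drug time: at least from the first post-enrolment dose to the end of Day 3, and longer if treatment began earlier. It also includes all pre-drug time back to birth. That is more than 30 days up to enrolment in strata 2 and 4, and possibly only days in strata 1 and 3. Nothing requires the selected value to come from before the first dose.

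The PK profile is taken around one of Study Assessment Doses 3 to 8 (Days 1 to 5). If Period 1 enters the GEE as one of the repeated outcomes, which neither document excludes, its neutropenia status may come from weeks before the exposure it is modelled against.

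**2. How the recorded status depends on test number.** Assumptions, none taken from the documents: each test has chance p of falling below the threshold; there is no drug effect; the lowest of k tests is recorded.

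- Independent tests: P = 1 − (1 − p)^k. For p = 0.10 and k = 7, this is 1 − 0.90^7 = 0.522.
- Correlated tests: each value is √ρ·b + √(1−ρ)·e, with b shared within the infant and b, e standard normal. The threshold is c = Φ⁻¹(p), which is −1.282 for p = 0.10. Then P = 1 − ∫ [1 − Φ((c − √ρ·b)/√(1−ρ))]^k φ(b) db. Simulation and numerical integration agree to within 0.2 percentage points.

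| p per test | Correlation ρ | k = 1 | k = 3 | k = 7 |
|---|---|---|---|---|
| 10% | 0 | 10% | 27.1% | 52.2% |
| 10% | 0.5 | 10% | 21.8% | 34.5% |
| 10% | 0.8 | 10% | 17.2% | 23.5% |
| 5% | 0.5 | 5% | 11.8% | 20.3% |
| 20% | 0.5 | 20% | 38.9% | 55.1% |

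Seven tests is about one a day, since Periods 2 to 6 last 7 days each. The same formula applies to the long baseline window: at p = 10% and ρ = 0.5, the share recorded as neutropenic in Period 1 is 29% with 5 tests, 40% with 10 and 52% with 20, against 10% with one.

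**Effect on an exposure comparison.** This was simulated with 32 infants, p = 20%, ρ = 0.5, 1 to 7 tests each and no drug effect, comparing AUC between infants with and without neutropenia by t test at the 5% level. The false-positive rate is 5% if test number is unrelated to AUC. It is 6%, 9% and 13% if the correlation between them is 0.3, 0.5 and 0.7.

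**The case against.** The strongest reply is that the endpoint is exploratory and the data collection is deliberately opportunistic. Extra blood cannot be taken from these infants only to count neutrophils, and seeking the worst value is a reasonable way to capture toxicity. That stands. It limits the importance of the point, but it does not explain why the baseline window should include on-drug counts or counts from birth.

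Three stronger readings are tempting and are not supported:

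- A reader might infer that infants with an early low count can no longer develop neutropenia in the analysis. No passage excludes infants who are neutropenic in Period 1 or defines an incident case. The GEE models status over time and does not by itself require a change from baseline.
- A reader might infer that the recorded value is always the worst. The rule accepts any value and asks only for an effort towards the most abnormal. The figures above therefore describe full success of that effort; partial success gives smaller and possibly site-dependent effects.
- A reader might infer that prior and drug-related neutropenia can never be told apart. The protocol records when ganciclovir began and the dosing since then, and hospital records remain source documents. Whether the eCRF stores laboratory dates cannot be seen, because the SAP offers the data dictionary and annotated CRFs only on request. The problem lies in the plan as written and may be recoverable.

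The exposure bias also needs test frequency to be correlated with AUC. That is plausible, but the documents do not show it.

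**Conclusion.** The point holds for the exploratory neutropenia objective. The Period 1 rule does not supply a pre-treatment count, and nothing in the protocol or SAP repairs that. This follows from the documents' own definitions and needs no assumption.

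The dependence on test number is certain in direction when the worst value is recorded, but its size is assumed. At 10% per test, moving from 1 to 7 tests takes recorded neutropenia from 10% to between 24% and 35% with within-infant correlation 0.8 to 0.5. The 52% for independent tests is an upper illustration, since serial counts in one infant are likely to be correlated. The inflation of a false exposure link is modest unless testing tracks AUC closely.

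The primary AUC12 endpoint and the sample size based on it are untouched. Protocol 11.4 and SAP Appendix B call neutropenia a secondary outcome, but the objectives and endpoints sections both class it as exploratory, and the point is weighed on that basis. The change is worth making because it is cheap.

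**What to change.** In Protocol 7.2.1, Appendix A footnotes c and e, and the matching footnotes in SAP section 6:

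- Define the baseline neutrophil count as the last clinical value before Treatment Dose 1, and record it as missing if there is none.
- Abstract dated clinical neutrophil counts from Treatment Day 1 to the end of follow-up.

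In Protocol 11.4 and SAP Appendix B:

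- Analyse on-treatment neutropenia against the PK measures with adjustment for the baseline count.
- Use the number of tests only in a sensitivity analysis. Testing can increase because counts are falling, so routine adjustment for it could remove part of a true exposure effect.

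The cost is modest extra chart abstraction and no additional blood. Sites already trace ganciclovir dosing back to the start of clinical treatment (Protocol sections 4 and 8.1.1), so the added period is largely the same. The drawback is that some infants will have no pre-treatment count and will be missing from, or need separate handling in, the baseline-adjusted analysis.
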